3.1 Study Design

OPTIN is a two-arm, parallel group, superiority randomised controlled trial (RCT) with blinded assessments. It includes a nested evaluation of the MCID of key outcome measures. All patients receive treatment, either a standardised package of physiotherapy exercise rehabilitation or the same exercise rehabilitation integrated with an exercise behaviour change intervention (OPTIN intervention). The primary outcome is the TUG measured at 12 months post-randomisation. All clinical outcomes are collected at baseline (0) and 4-, 8- and 12-months following randomisation.

The trial will take place in at least 6 NHS hospitals across the UK and their related physiotherapy services and via video-call in participant homes. Each site will recruit participants, undertake measures and provide the intervention and comparator. A trial research clinician (TRC) will collect

data at research assessments, following a standardised format and using outcome measures that are valid and reliable with this patient population. Measures are a mix of self-report questionnaires and measures of physical function, including monitoring adverse events and intervention adherence.

3.2 Eligibility

Participants will be adults aged 55 years or over who have a diagnosis of at least one vertebral fragility fracture due to osteoporosis and back pain who are willing and able to give informed consent. Specifically:

Inclusion Criteria

- Men and women ≥ 55 years: all women at least 1 year post-menopausal
- One or more VFFs confirmed by radiography, X-Ray, MRI or DEXA scan, people with VFF of any severity and at any time-point post-fracture are eligible
- Back pain in the previous 12 months
- Able to walk at least 10 metres independently with or without a walking aid

Exclusion Criteria

- Conditions that would make participating in physiotherapy or exercise unsafe or confound results e.g., significant neurological and psychiatric conditions, severe unstable cardiovascular or pulmonary disease
- Bone loss secondary to other metabolic disorders, diseases or medications e.g., rheumatoid arthritis, anorexia
- Primary problem is back pain that involves pain radiating into the lower limbs

3.3 Sample size

The primary outcome is the TUG test, a test of balance, lower limb strength and walking ability with established reliability and validity. It records the time in seconds (s) a person takes to stand up from a chair, walk 3 metres at a self-selected speed, turn and walk back and sit down, faster performance indicates better function. [10, 15] The MCID for the TUG has not been established in people with VFFs, but a MCID of 1.4 s is reported for similar older populations with chronic musculoskeletal disorders.[22] The study requires 104 participants (52 per arm) to be 80% powered to detect a 1.4s difference in TUG score between groups at a 5% significance level (two sided) assuming that the SD is 2.5s. Similar trials have had loss to follow-up rates of 10% at 12 months. To account for this the sample size is 116 participants (58 per arm).

Sample size calculations were performed in Stata v15 (StataCorp. 2017. *Stata Statistical Software: Release 15*. College Station, TX: StataCorp LLC).

3.4 Randomisation and blinding

Following screening and confirmation of eligibility, baseline assessment and registration participants will be individually randomised (1:1) between either: OPTIN intervention or comparator

(physiotherapy exercise rehabilitation) trial arms. The computer-generated randomisation schedule will be prepared by the trial statistician (RK). Individual randomisation will be stratified by recruitment centre and permuted blocks of varying undisclosed sizes will be used. Full details of randomisation, concealment and allocation procedures are available in the OPTIN protocol version 4.0, 4th March 2022, stored in the trial master file (TMF.)

The TRC and study personnel conducting measures and entering data will be blinded to allocation group. Due to its nature as an exercise and behaviour change intervention, participants and those physiotherapists delivering the rehabilitation will be aware of treatment allocation and hence a codebreaking facility is not required. To reduce contamination, treating physiotherapists will be allocated to one arm of the trial, provided with the training and resources for this arm alone, and only deliver treatments to participants allocated to this arm.

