5.6 Reliability

To ensure consistency and reliability of data processing, validation checks will be conducted. This will include checking for duplicate records, checking for missing data, checking the validated values for implausible values and validating potential outliers, and checking that data has been imported into statistical packages correctly. This will involve records from each site. Calculations and processes performed by computer e.g., QUALEFFO-41 calculations will be checked by hand calculations. These checks will be performed for 25 participants randomly sampled from the dataset. Clarification will be sought by comparing electronic datasets with case report forms.

6. Analysis

6.1 Methods used for analysis of primary outcome.

We will plot and display TUG data at all time points: 0, 4, 8 and 12-months to consider patterns of change over time and any outliers. At 12-months post-randomisation the two treatment groups will be compared on the primary outcome of the TUG measure using a multivariate linear regression model adjusting for recruiting centre (stratification factor), age at baseline and baseline TUG score. An unadjusted t-test will also be undertaken. As the TUG is recorded at 4 months and 8 months after randomisation as well, an additional analysis utilising all time points using multi-level modelling and including a treatment by time interaction, if appropriate, will be undertaken. For each of these models, the assumption of approximate normality will be assessed by examining the residuals. If this assumption is not met the first approach will be to consider a transformation to achieve normality. If this is not possible, the two groups will be compared using non-parametric methods (e.g., Mann-Whitney U-test). This analysis will be unadjusted and will consider each time point separately.

TUG (seconds)*	Intervention Mean (SD)	Control Mean (SD)	Mean difference (95% Cl)	p-value
Unadjusted 12- months				
Adjusted for baseline, centre and age				
Supporting analyse	25			
Repeated measure	S			
4 months				
8 months				
12 months				
12 months (per protocol)				

Table 11: Analysis of primary endpoint, TUG test change at 12-months

* A negative change corresponds to a better result at 12-months

6.2 Methods used for analysis of secondary outcomes.

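### Physiotherapists are nested within arm, but no planned analysis allows for therapist clustering; if the therapist ICC exceeds zero, the primary 95% CI is too narrow

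*SAP*

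**What the plan says.** SAP section 3.4 randomises participants individually within centre. To limit contamination, "treating physiotherapists will be allocated to one arm of the trial, provided with the training and resources for this arm alone"; they also "only deliver treatments to participants allocated to this arm". Section 3.5 describes a therapist-delivered treatment: an assessment and six follow-up sessions in both arms. The OPTIN arm adds an extended interview and at least three behavioural techniques, which the physiotherapist selects from nine.

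Section 3.3 gives the power statement: "The study requires 104 participants (52 per arm) to be 80% powered to detect a 1.4s difference in TUG score between groups". The other inputs are an SD of 2.5 s and a two-sided test at 5%. An allowance for 10% loss raises 104 to 116. No ICC, number of participants per therapist or design effect appears.

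The primary analysis in section 6.1 (outlined in 3.8) is a "multivariate linear regression model adjusting for recruiting centre (stratification factor), age at baseline and baseline TUG score". It has no therapist term and no cluster-robust standard error. The one multi-level model in section 6.1 is for the repeated time points. Table 11 has no row for a therapist analysis.

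**The concern.** Individual randomisation makes participants comparable at entry, but it does not keep their outcomes independent once a shared therapist treats several of them. Because each therapist works in one arm only, variation between therapists adds to the variance of the between-arm contrast. The treatment leaves room for such variation, since it relies on an interview and on techniques that the therapist chooses.

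The centre term does not remove it. Within a centre the two arms have different therapists, so the difference between those therapists stays in the treatment estimate. Adjusting for baseline TUG reduces the residual variance but leaves the therapist variance untouched. The model's standard error then falls by more than the true one.

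What is at stake is the validity of the primary p-value and 95% CI. If the primary result is close to the 5% threshold, nothing planned would show whether it survives allowance for therapist. A therapist analysis chosen after the results are known would be open to dispute.

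**Working it through.** **Inputs from the SAP.** Difference 1.4 s, SD 2.5 s, two-sided 5%, 52 evaluable per arm, 10% loss (section 3.3); at least six hospitals (3.1).

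**Assumptions, not in the SAP.** Therapist ICC of 0.01, 0.02 or 0.05. Either 12 therapists (one per arm at six sites) or 24 (two per arm at six sites).

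**1. The plan's own figure.** The normal approximation gives n = 2 × (1.96 + 0.842)² × (2.5/1.4)² = 50.1, so 51 per arm. With the noncentral t, power is 0.7997 at 51 and 0.807 at 52, so 52 per arm. 104/0.9 = 115.6, so 116. Both stated numbers reproduce, with independent observations (a design effect of 1).

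**2. Design-effect formula.** m = 52/(therapists per arm), which is 8.67 or 4.33, and DE = 1 + (m − 1) × ICC. The true SE is √DE times the assumed one. Type I error = 2 × [1 − Φ(1.96/√DE)]. Power = Φ(0.56 × √(26/DE) − 1.96), where 0.56 = 1.4/2.5 and 26 = 52/2. With DE = 1 this gives 0.81.

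| Therapists | ICC | DE | SE ratio | Type I error | Power, unadjusted |
|---|---|---|---|---|---|
| 12 | 0.01 | 1.08 | 1.04 | 5.9% | 0.79 |
| 12 | 0.02 | 1.15 | 1.07 | 6.8% | 0.76 |
| 12 | 0.05 | 1.38 | 1.18 | 9.6% | 0.68 |
| 24 | 0.01 | 1.03 | 1.02 | 5.4% | 0.80 |
| 24 | 0.02 | 1.07 | 1.03 | 5.8% | 0.79 |
| 24 | 0.05 | 1.17 | 1.08 | 7.0% | 0.75 |

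**3. Simulation of the planned type of model.** The formula leaves out centre and baseline. A regression with centre fixed effects and baseline, ignoring therapist, was therefore simulated with 104 participants, six centres and 12 therapists (age was left out). For baseline to 12-month correlations of 0 and 0.5, type I error was about 5% at ICC 0, about 6–7% at 0.01, about 7% at 0.02 (7.0% and 7.3% in 10,000 runs) and about 10–12% at 0.05 (9.5% and 11.9%). The higher values go with the stronger baseline correlation, so baseline adjustment does not cure the problem and slightly worsens it.

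**4. Power with baseline adjustment, 12 therapists.** At an assumed correlation of 0.5, the factor DE becomes (1 − 0.25) + 7.67 × ICC if the ICC is a share of total variance. That is 0.827 at ICC 0.01 and 1.133 at 0.05, giving power of 0.88 and 0.76. If the ICC is instead conditional on baseline, the factor at 0.05 is 0.75 × 1.383 = 1.037 and power is 0.80. The correlation needed to offset the loss fully lies between √(1 − 1/DE) and √(7.67 × ICC): 0.37–0.39 at ICC 0.02 and 0.53–0.62 at ICC 0.05. These are normal approximations and ignore the few degrees of freedom.

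**The case against.** The case on the other side is that the size, and perhaps the existence, of the problem is unknown. The package is standardised and lasts 16 weeks. The outcome is a timed test at 12 months, roughly eight months after treatment ends, taken by a blinded assessor. A therapist ICC near zero is possible. Twelve therapists is close to the unfavourable end, since section 3.1 allows more than six hospitals together with their related physiotherapy services. With 24 therapists and ICC 0.01–0.02 little changes. All of this stands, and it is why the point is conditional.

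A reader might infer more than the SAP supports:

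- **That the CI is certainly too narrow and power certainly below 80%.** Both depend on an ICC and a therapist count that the SAP does not give. On power, the section 3.3 calculation also takes no credit for the planned baseline adjustment, which may recover the loss.
- **That one unusually good or poor therapist could pass for a treatment effect.** At ICC 0.05 the therapist SD is 2.5 × √0.05 = 0.56 s. With six equal-sized therapists per arm, one lying 2 SD from the mean shifts the arm mean by 2 × 0.56/6 = 0.19 s, against a target of 1.4 s. The concern is understated uncertainty, not one therapist producing the result.
- **That the primary model must be replaced.** With 12 therapists and centre fixed, about 12 − 6 − 1 = 5 degrees of freedom remain for treatment, and the therapist variance would be poorly estimated. Making that model primary is a debatable trade.

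None of this answers the core point: the SAP itself creates the nesting and plans no analysis that would show whether it matters.

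**Conclusion.** The point holds in conditional form. Therapist is nested within arm by design, the sample size and primary model assume independence, and no planned analysis addresses therapist clustering. If the therapist ICC exceeds zero, the primary interval is too narrow and the type I error is above 5%, whatever the centre and baseline adjustment.

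Under the assumed ICC range of 0.01–0.05, the inflation runs from negligible (about 5.4%, 24 therapists, ICC 0.01) to material (about 10–12%, 12 therapists, ICC 0.05). Power on the SAP's unadjusted basis would be 0.79–0.68 with 12 therapists or 0.80–0.75 with 24, but a shortfall under the planned adjusted model is not established. This is a low-cost improvement to the plan; it does not invalidate the primary analysis.

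**What to change.** Keep the current primary model and make these changes:

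1. In section 6.1 and Table 11, add a prespecified sensitivity analysis of 12-month TUG: the primary model plus a random intercept for the main treating physiotherapist (nested in centre and arm), fitted by REML with Kenward-Roger degrees of freedom. Report the therapist ICC and the number of therapists per arm.
2. Confirm that the treatment logs identify the therapist. Sections 3.6 and 5.3 mention attendance and treatment logs, but not therapist identity. Define the main therapist for participants treated by more than one, since the SAP does not say that one therapist delivers all sessions.
3. In section 3.3, state that the 80% power assumes no therapist clustering.

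The cost is SAP wording and, if the logs hold it, one extra data field; no further participants are needed. The downside is a wider interval on few degrees of freedom (about 5 with one therapist per arm at six sites and centre fixed) and an imprecise therapist variance, which may be estimated at zero. An estimate of zero should not be read as proof that therapists do not differ.

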3.5 Treatment Interventions per Allocated Arm

OPTIN Intervention	Standardised physiotherapy exercise rehabilitation:				
	Physiotherapy musculoskeletal assessment (60 mins)				
	• Six follow-up sessions (30 mins each) over 16 weeks				
	Extended assessment (additional 30 mins) comprising Personalised Exercise Questionnaire (PEQ); self-report questionnaire about exercise behaviours and extended interview to assess capability (C), opportunity (O) and motivation (M) regarding exercise behaviours (B), (COM-B). (Integrated with 60 min assessment above)				
	Individualised prescription of techniques to support exercise behaviour. At least 3 techniques, selected by physiotherapist from a toolkit of 9 recognised techniques (60 mins total, spread over 16 weeks).				
Comparator	Standardised physiotherapy exercise rehabilitation:				
	Physiotherapy musculoskeletal assessment (60 mins)				
	• Six follow-up sessions (30 mins each) over 16 weeks				

Table 2: Summary of Intervention and Comparator Treatments

3.6 Outcome Assessment Schedule

At the baseline assessment information is collected about relevant demographic characteristics and past medical history including fragility fractures, falls in previous year, bone mineral density (BMD) and co-morbid conditions using the weighted Functional Co-morbidities Index. [23] The participant is then asked to complete the outcome measure package, this is then completed again at 4, 8 and 12 months plus the adherence (EARS-B: 4, 8, 12 months) and global rating of change (GRC: 4 months) scales which can only be completed post-treatment. Session attendance is logged by physiotherapists across the intervention period.

Table 3: Outcome Measure Time-points

MEASURES	Month-0	Month-4	Month-8	Month-12
----------	---------	---------	---------	----------

Falls in past year	✓			
Falls (prospective		~	~	~
log)				
NPRS (back pain last	\checkmark	\checkmark	\checkmark	\checkmark
2 weeks)				
Thoracic kyphosis	✓	~	~	~
TUG	✓	~	✓	✓
FR	√	\checkmark	✓	✓
TLS	✓	\checkmark	✓	~
QUALEFFO-41	✓	✓	✓	~
SEE	✓	✓	✓	~
FES-I	✓	~	✓	~
EQ-5D-5L	✓	~	✓	✓
EARS-B		✓	✓	~
6 MW	✓	~	✓	 ✓
Grip strength	✓	~	✓	 ✓
Healthcare use		✓	✓	\checkmark
(prospective log)				
Adverse Events		~	~	✓
GRC		~		

3.7 Quality Control and Data Validation

Data will be collected from participants and the research team onto paper questionnaires/CRFs at research assessment visits. The originals will be scanned, and then sent by a member of the local research team to the study coordinating office in Oxford by post, using a Freepost account, keeping a copy at site and sending a copy electronically via secure NHS networks. Upon receipt of questionnaires/CRFs, appropriate data quality and validation checks will be carried out by the study research administrator and the data entered into a study-dedicated databases.

3.8 Statistical Analysis Outline

It is anticipated that all statistical analysis will be undertaken using Stata (StataCorp LP, www.stata.com) or other well-validated statistical packages such as SPSS. A blinded analysis of the data (not separated by treatment group) will be undertaken prior to the final data lock to look into the distribution of variables, missing data distributions, and to finalise the per protocol population.

Standard descriptive statistics will be used. Means and standard deviations (SDs) or medians (with lower and upper quartiles) as appropriate will be used for continuous variables, and numbers and percentages will be used for binary and categorical variables. Summary statistics will be presented for all comparative outcomes, and effect estimates will be reported together with 95% confidence intervals with all tests carried out at a 5% two-sided significance level.

The final analysis of all primary and secondary endpoints will be conducted together when all recruited patients have completed all follow-up. The study sample will be described, and then principal comparisons will be performed on an intention-to-treat basis, with a per-protocol analysis repeated at 12 months for the primary outcome, the Timed up and Go (TUG) test.

At 12 months post-randomisation the two treatment groups will be compared on the TUG measure using a multivariate linear regression model adjusting for recruiting centre (stratification factor), age and baseline TUG score. An unadjusted t-test will also be undertaken. An additional analysis utilising all time points will be undertaken. The assumption of approximate normality will be assessed by examining the residuals. If this assumption is not met the first approach will be to consider a transformation to achieve normality. If this is not possible, the two groups will be compared using non-parametric methods (e.g., Mann-Whitney U-test).

Similar analyses will be performed for secondary outcomes which can be considered approximately continuous (QUALEFFO-41, FES-1, NPRS, TLS, Grip strength, 6MW, FR, Thoracic kyphosis, SEE and EARS) at 4-, 8- and 12-months post-randomisation. The appropriateness of the assumption of approximate normality will also be considered and transformation to normality or non-parametric methods used as appropriate. It is not anticipated that the data about healthcare visits or falls will be approximately normally distributed, therefore, this data will be summarised by treatment group using medians and IQRs and compared using non-parametric methods. Data about falls will also be included in safety data reporting e.g., fall nature and severity (see section 7 below).

4. Statistical Principles

4.1 Statistical Significance and Multiple Testing

A two-sided 5% significance level will be used throughout with 95% CIs presented. Since there is a single primary outcome in this study there is no concern regarding multiple testing, and all secondary outcomes will be considered as supporting the primary result.

4.2 Definition of Populations for Analysis

All analyses will be performed for the intention to treat (ITT) population. This will include all randomised participants with available data who will be analysed according to their allocated intervention regardless of the treatment they received.

In addition, analysis of the primary outcome (TUG at 12 months) will be repeated for the per protocol (PP) population which will include only those participants who received their allocated treatment, that is the participants in the intervention arm that receive the OPTIN assessment interview and at least 3 adherence techniques and the participants in the comparator arm that do not. Participants with other major protocol deviations (e.g., recruited and later found to be ineligible) will also be excluded from this population.

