Conservative treatment for osteoporosis includes bone protective medications and lifestyle adaptations.[3] Guidelines recommend people with osteoporosis keep active and exercise to slow the rate of bone loss, to maintain muscle strength and physical function and to prevent falls and further fractures.[2-5] Multiple randomized controlled trials (RCTs) have investigated the efficacy of exercise for people with VFFs and reported short-term, post-treatment benefits to pain, strength, spinal posture, balance, fear-of-falling, mobility and QoL. [4-6] A Cochrane systematic review in 2019 concluded there is moderate-quality evidence that exercise improves physical function.[4] However, treatment effects are often small and difficult to sustain. [4, 6] Adherence, or the extent to which patients engage in treatment, has been identified as an important issue by many studies, with adherence to clinic-based exercise protocols often around 50% and lower for unsupervised home exercise. [4-7] Partial or non-adherence is associated with worse outcomes and conversely higher adherence with better outcomes. [4, 6, 7] Adherence is a critical consideration because it affects exercise dose. For example, in the PROVE trial benefits associated with exercise at 4 months were not sustained at 12 months, whilst those who attended more sessions experienced better outcomes.[6] Higher adherence has been associated with greater treatment effects but studies monitoring adherence show exercise compliance declines after supervised interventions cease. [7, 8] When assessing intervention efficacy, it is also important to know the minimal clinically important difference (MCID) of any outcome measure in the population concerned, which is defined as the smallest difference in score which a patient perceives as beneficial.[9] A recent Cochrane review identified the Quality-of-Life Questionnaire (QUALEFFO-41) and the Timed Up and Go (TUG) test as important outcome measures targeted by exercise interventions in people with VFFs and also recognised that their MCIDs were unknown.[4]

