5.3 Description of Compliance with Intervention

Treatment fidelity will be reported. The total number of trial physiotherapy sessions attended, and the number of these that were delivered virtually will be summarised for each group. Compliance with the intervention is defined as participating in the assessment and prescription of at least 3 adherence support techniques as recorded on treatment logs. Treatment session numbers and as well as the adherence strategies prescribed for the intervention group. We will display graphically the types and frequency with which adherence strategies were selected (Figure 2). We will summarise participant visits to healthcare professionals outside of the OPTIN trial, and those related to back pain to monitor total dose of physiotherapy (private and NHS) and back-related intervention, see Table 8.

		Intervention		Contr	ol
	Physiotherapy Session	Virtual session	Behavioural Techniques	Physiotherapy Session	Virtual session
	n	n	n	n	n
Assessment*					
Follow-up 1					
Follow-up 2					
Follow-up 3					
Follow-up 4					
Follow-up 5					
Follow-up 6					
Total (median IQR)					
Compliant n (%)					
Assessment and ≥ 3 techniques					

Table 7: OPTIN sessions attended and compliance.

*Extended 90 min for OPTIN arm. Virtual session = physiotherapy via telephone or video-call.

Figure 2. Adherence strategies selected (example)

Information about health care received outside of the trial i.e., number of health care visits, reason for visit (back related/ un-related), health professional seen (GP/Nurse/Physiotherapist/OT/Other), hospital stays is not expected to be normally distributed. Total visit numbers, number of physiotherapists visits, (private and NHS) reason for visit (back related/ unrelated) will be summarised for each group.

	Total	Intervention	Control
	n (%) median (IQR)	n (%) median (IQR)	n (%) median (IQR)
Number of health			
professional			
appointments			

Number of back-related		
appointments		
Number of		
physiotherapist		
appointments		
Private physiotherapist		
appointments		
NHS physiotherapist		
appointments		

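### The per-protocol set screens on treatment received in the intervention arm only, so the supporting TUG comparison is expected to lean towards the intervention

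*SAP*

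**What the plan says.** Section 4.2 makes intention to treat the basis of all analyses and repeats the 12-month TUG analysis in a per-protocol population "which will include only those participants who received their allocated treatment". It then defines that phrase by arm, as those allocated to OPTIN who "receive the OPTIN assessment interview and at least 3 adherence techniques and the participants in the comparator arm that do not". A further sentence reads: "Participants with other major protocol deviations (e.g., recruited and later found to be ineligible) will also be excluded from this population".

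Other sections bear on this:

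- **Section 3.5 (Table 2).** Both arms are offered a 60-minute assessment and "Six follow-up sessions (30 mins each) over 16 weeks". The intervention arm also has an extended assessment and at least three behavioural techniques ("60 mins total, spread over 16 weeks").
- **Section 5.3.** "Compliance with the intervention is defined as participating in the assessment and prescription of at least 3 adherence support techniques". No counterpart is given for the comparator. Table 7 counts control sessions but sets no threshold for them.
- **Section 2.1.** In an earlier exercise trial in this field, the benefit at 4 months was not sustained at 12 months, "whilst those who attended more sessions experienced better outcomes".
- **Section 3.8.** "A blinded analysis of the data (not separated by treatment group) will be undertaken prior to the final data lock", one purpose being to finalise the per-protocol population.
- **Table 11.** The per-protocol row is listed under supporting analyses.

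**The concern.** A per-protocol comparison is already non-randomised. It is least misleading when whatever is screened on is screened in the same way in both arms. Here the intervention arm must show that it took up treatment, whereas the comparator arm need only show that it did not receive the other arm's extra components. Participants who disengage are therefore dropped from one arm and kept in the other.

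In a trial of adherence support, willingness to attend is close to the trait under study, and the SAP itself expects it to go with outcome. A difference in the per-protocol row could then reflect who was kept rather than what the support did. That row is reported in the same table as the primary result and is the only planned analysis by treatment received.

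**Working it through.** **1. The plan's own figure.** Section 3.3 uses a difference of 1.4 s, SD 2.5 s, 80% power and two-sided 5%. A two-sample t-test calculation gives 51.03, rounded up to 52 per arm or 104 in all. Then 104 / 0.9 = 115.6, rounded up to 116. The sample size reproduces. The SAP gives no figure for the per-protocol set.

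**2. The rule applied to like participants** (assuming no other major deviation):

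| Participant | Intervention arm | Comparator arm |
|---|---|---|
| Attends nothing | Excluded | Meets the wording |
| Attends the assessment, stops before three techniques are prescribed | Excluded | Meets the wording (no techniques apply) |
| Attends the assessment, three techniques prescribed there, then stops | Included | Meets the wording |
| Attends throughout, three or more techniques | Included | Meets the wording |

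The arms differ in the first two rows. The third row shows that the intervention rule is only a partial screen on attendance.

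**3. Size under no treatment effect.** Let p be the share who meet, or would meet, the intervention rule. Let D be their 12-month TUG advantage over the rest, in seconds, after the model's adjustment for centre, age and baseline TUG. Randomisation makes p and D the same in both arms in expectation. Write m1 for the mean TUG of those who meet the rule and m0 for the rest, so m1 - m0 = -D.

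- Intervention per-protocol mean: m1
- Comparator per-protocol mean: p x m1 + (1-p) x m0
- Difference: (1-p) x (m1 - m0) = -(1-p) x D

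A negative value favours the intervention. Neither p nor D is in the SAP. Section 2.1 cites clinic adherence of around 50%, but that refers to exercise protocols and does not estimate p. Assumed values give these biases in favour of the intervention (percentage of 1.4 s in brackets):

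| p | D = 0.5 s | D = 1.0 s | D = 2.0 s |
|---|---|---|---|
| 0.9 | 0.05 s (4%) | 0.10 s (7%) | 0.20 s (14%) |
| 0.8 | 0.10 s (7%) | 0.20 s (14%) | 0.40 s (29%) |
| 0.7 | 0.15 s (11%) | 0.30 s (21%) | 0.60 s (43%) |
| 0.6 | 0.20 s (14%) | 0.40 s (29%) | 0.80 s (57%) |

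**4. Effect on the nominal 5% test.** This uses a normal approximation with 52p against 52 participants and SD 2.5 s.

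- p = 0.8, D = 1.0 s: SE = 2.5 x sqrt(1/41.6 + 1/52) = 0.52 s; bias 0.20 s; false-positive rate about 6.7%.
- p = 0.7, D = 1.4 s: SE = 2.5 x sqrt(1/36.4 + 1/52) = 0.54 s; bias 0.42 s; false-positive rate about 12%.
- p = 0.9, D = 0.5 s: bias 0.05 s; false-positive rate about 5.1%, in effect nominal.

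**5. A common rule.** If the same criterion applied in both arms and selected the same kind of participant, this term would be zero under no effect.

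**The case against.** The strongest reply is that the governing phrase limits the set to those who received their allocated treatment. Section 3.5 defines comparator treatment as an assessment and six sessions, so a complete non-attender did not receive it. The clause on other major deviations is also open-ended. This shows that the team may have intended a comparator condition, but none is written: the explanatory clause fixes the meaning of the phrase, and the only example of another deviation is ineligibility.

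Second, a reader might infer that the rule compares motivated attenders with all comers. The SAP does not support that. No minimum number of sessions is set, and Table 7 allows techniques to be recorded at the assessment. The physiotherapist selects the techniques, so failing the rule may reflect delivery rather than disengagement. Techniques might also be added for participants who struggle. Section 2.1 speaks of sessions attended, not techniques prescribed. All of this stands and weakens the expected bias. It does not remove the asymmetry for those who attend nothing.

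Third, the analysis uses available cases (section 4.3). If disengaged participants more often lack a 12-month TUG, fewer of them remain in the comparator set and the gap narrows. This also stands.

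Fourth, a reader might infer that a rule differing by arm makes the blinded review in section 3.8 impossible. It does not. The rules can be settled, and membership flagged from treatment logs, without anyone seeing TUG by arm. What the text lacks is a statement that this is what is meant.

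**Conclusion.** The concern holds in limited form. As written, section 4.2 screens on receipt of treatment in one arm only. Given the SAP's own link between attendance and outcome, the supporting per-protocol TUG comparison is expected to lean towards the intervention. The direction is an expectation: it requires those who meet the rule to do better for reasons other than the adherence support. The size is illustrative only, from near zero (0.05 s) to about 0.8 s over the assumed range, because p and D are assumptions.

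The primary result is unaffected, since intention to treat is the principal analysis and per protocol is only supporting. A reader might go on to infer that the row could be used to rescue a null primary result. Nothing in the SAP gives it that role, and the point does not depend on it. It remains worth correcting because a stated rule that yields a tilted comparison is more than a missing detail.

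**What to change.** **Section 4.2.** Define receipt of allocated treatment by one minimum-treatment criterion, taken from the treatment logs and applied identically in both arms. The trial team should set the threshold before any data are seen by arm. Keep absence of the OPTIN components as an additional condition for the comparator. Label the result as a non-randomised comparison.

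**Sections 4.2 and 6.1, Table 11.** Add, or use in place of the per-protocol row, a complier-average causal effect estimate: two-stage least squares with allocation as the instrument for receiving the interview and at least three techniques, and the same covariates as the primary model.

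**Section 3.8.** State that the blinded review settles the per-protocol rules without access to outcomes by arm.

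**Cost.** SAP wording only, as session attendance and techniques are already logged. Each remedy has a limit that should be stated:

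- The complier-average interval is about 1/p times as wide as the intention-to-treat interval (1.1 times at p = 0.9, 1.7 times at p = 0.6).
- The complier-average estimate assumes that allocation affects TUG only through full receipt. This fails if the interview alone, or one or two techniques, has an effect.
- A set based on common attendance still conditions on something that happens after randomisation and that adherence support may itself change.
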